- Population:** Up to 1,000 participants¹ (male and female adults ≥ 18 years of age and male and female children < 18 years of age) with possible or definitive infection and/or close contacts to patients with possible or definitive infection with Pathogen "X" will be enrolled into one of two patient groups. Suspected cases may be based on appropriate exposure history and/or clinical presentation. Enrollment will be stratified by disease severity or other major categories of disease presentation as applicable.
- Group 1: Adults or children with confirmed or suspected Pathogen "X" infection representative of the disease spectrum
- Group 2: Adult or child close contacts of Pathogen "X" confirmed and/or suspected cases enrolled in Group 1
- Number of Sites:** Up to ten VTEU sites
- Study Duration:** Approximately 2 years from implementation of field activity through closure and analysis
- Participant Duration:** 12 months
- Objectives:** Primary:
- To characterize Pathogen "X" binding and neutralizing antibody responses by age and disease severity in study subjects.
 - To characterize T cell responses by age and disease severity.
 - To characterize B cell responses by age and disease severity.
 - To describe the clinical presentation and outcomes of Pathogen "X" infection in study subjects.

¹ Number of participants may be adjusted based on statistical considerations of Pathogen "X" and clinical manifestation.

Secondary:

- To describe innate immune responses to Pathogen “X”.
- To collect specimens for isolation of Pathogen “X” from body compartments pertinent to the pathogen.
- To determine rates of Pathogen “X” infection among close contacts of infected patients enrolled in Group 1.
- To determine the persistence of Pathogen “X” in whole blood, serum, urine, saliva, stool, or other body fluids as available (e.g., semen, vaginal secretions, breast milk) and characterize modes of pathogen shedding to support the development of diagnostic assays and public health prevention policy around transmission risk.

Exploratory:

- To characterize Pathogen “X”-specific immune responses other than classical antibody and T cell responses following Pathogen “X” infection to support vaccine development.
- To make available to the scientific community well-characterized specimens from Pathogen “X”-infected study subjects to facilitate development of diagnostic tests, vaccines, and therapeutics for use in other Pathogen “X” research.

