- To collect large numbers of blood immune cells by leukapheresis from selected participants to establish a specimen bank for future detailed Pathogen “X” immunological studies.
- To evaluate the associations of Pathogen “X”-specific humoral and cellular immune responses with Pathogen “X” in whole blood, serum, exosomes, urine, saliva, stool and/or other body fluids as available (e.g., semen, vaginal secretions, breast milk).
- To sequence Pathogen “X” from collected specimens (blood, body compartments specific to Pathogen “X”, etc.) in a subset of participants for the study of within-host pathogen evolution.

Description of Study Design:

[figure not shown]
This is a prospective, observational, noninterventional cohort study designed to collect clinical information and specimens to evaluate innate and adaptive immune responses of patients with confirmed Pathogen “X” and their close contacts.

Estimated Time to Complete Enrollment:

2 years. This protocol will be shelf ready for specimen collection from potentially emerging pathogens over the life cycle of the current IDCRC.

SCHMATIC OF STUDY DESIGN

Total N: Up to 1,000 participants enrolled into one of two patient groups

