4. STUDY DESIGN

This is a prospective, observational, noninterventional cohort study designed to collect clinical information and specimens to evaluate the innate and adaptive immune responses from up to 1,000 study participants. Both males and females will be screened for study interest and eligibility and enrolled, adults ≥ 18 years of age and children < 18 years of age. Two types of participants will be recruited:

- Group 1: Patients with confirmed or suspected Pathogen “X” infection, and
- Group 2: Close contacts of patients with confirmed and/or suspected Pathogen “X” infection enrolled in Group 1.

The study will ensure enrollment of patients that have clinical symptoms representative of the disease spectrum.

Group 1

Baseline data will be collected from participants with confirmed or suspected Pathogen “X” infection including demographics/sociodemographics, medical history, exposure history, medications, signs/symptoms and symptom onset date to determine the days post-illness onset (DPO). Specimens will be collected from body compartment specific to Pathogen “X”. Specimens may include whole blood, serum, urine, saliva, stool or other body fluids as available (e.g., semen, vaginal secretions, breast milk) depending on the specifics of Pathogen “X”. Specimens may be salvaged if available from standard of care testing. Clinical information and specimens will be collected at enrollment and then at an interval determined by the biologic characteristics after enrollment (up to 12 months). See Section 6 Study Procedures/Evaluations.

The association between age, severity of illness, and duration of illness on Pathogen “X” immune responses will also be explored.

An optional study visit will be conducted between DPO 30 and 90 in adult participants from Group 1 who volunteer to undergo leukapheresis. Leukocytes will be selectively harvested; red cells and other blood components will be returned to the patient. Participation will be offered to all patients and volunteers will be accepted until the spots are filled. In a typical 1½ to 3-hour leukapheresis procedure, approximately 5×10^8 to 1×10^{10} cells can be isolated with only minimal loss of red blood cells. No sedation is required. The procedure will be done by trained staff at the study site and will be done using devices and procedures that conform to standard guidelines and SOPs.

Identification of close contacts will take place as soon as possible after Group 1 participants are enrolled.

Group 2

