5. STUDY POPULATION

5.1 Selection of the Study Population

Up to 1,000 male and female participants, adults ≥ 18 years of age and children < 18 years of age, will be screened to enroll participants who meet all eligibility criteria and agree to participate.

Patients will be recruited from 10 VTEU sites and/or their sub-sites. Sites can enroll from either outpatient or inpatient sites, or both. Enrollment will be stratified by disease severity or other major categories of disease presentation as applicable. Pregnant women will not be excluded from enrollment. Blood collection volumes will be adjusted accordingly for these participants. There will not be a required sample size for this population. As this study is a descriptive study, sample size is based on feasibility instead of power for hypothesis testing.

- Group 1: Patients with confirmed or suspected Pathogen “X” infection, and
- Group 2: Close contacts of patients with confirmed and/or suspected Pathogen “X” infection enrolled in Group 1.

A subset of 10-20 adult volunteers from Group 1 will undergo leukapheresis during follow-up to compare immunological responses in those with variable severity and also to allow future comparisons with those receiving Pathogen “X” vaccines (enrolled in other studies). Study staff will inform potential participants/legally authorized representatives (LAR) of the study, obtain informed consent, and determine study eligibility. Individuals who meet all study eligibility criteria and agree to participate will be enrolled.

Usual clinical management at VTEU outpatient or inpatient sites, including standard medical care and standard therapy, will not be modified because of the study. All participants will receive appropriate treatment for Pathogen “X” that is accepted by medical experts as standard of care for the specific institution and is widely used by healthcare professionals.

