7. STATISTICAL CONSIDERATIONS

7.1 Study Hypotheses and Design

The overall objective of this prospective observational cohort study is to characterize the natural history and immune responses to Pathogen “X” infection in patients who present varying levels of disease severity and clinical symptoms, and in their close contacts. The study hypothesizes that Pathogen “X” elicits broad immune responses in individual patients, and that these responses vary over time during infection and as disease severity and symptoms progress. The study will determine whether immune responses associated with disease severity, symptoms, and demographic variables. In particular, it will focus on association with age, and consider other known or suspected factors that associate with immune responses (e.g., sex). It will also characterize spread of infection among close contacts of Pathogen “X” infected patients.

To address its objectives with adequate power, the study will target enrolling approximately 1,000 Pathogen “X” infected or suspected children and/or adult patients (Group 1) and children and/or adult close contacts of the Pathogen “X” infected patients who are enrolled in Group 1 (Group 2). Participants in Group 1 will be representative of the Pathogen “X” disease spectrum.

The primary statistical analysis of data from participants enrolled in Group 1 will be conducted using the most severe level of care (hospitalized ICU, hospitalized non-ICU, outpatients not hospitalized) received by each study participant. Secondary statistical analyses will be performed using additional disease severity scales if developed (see Appendix B).

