7.3 Participant Enrollment and Follow-Up

We anticipate that the study will complete enrollment in Group 1 within approximately X months upon opening. Given that many sites will enroll participants for the study, it is reasonable to expect that recruitment will be completed in fewer than X months. Every patient in Group 1 will be followed for about X years.

Subjects with close contact exposure to patients with confirmed or suspected Pathogen "X" in Group 1 and who meet the inclusion criteria will be enrolled in Group 2. We anticipate that the study will enroll 1000 participants in Group 2 (i.e., an average of 1.5 to 2 close contacts per patient enrolled in Group 1). We expect that the study will complete enrollment in Group 2 within approximately X months upon opening. Every patient in Group 2 will be followed for about X days/weeks/months.

The age of participants will be monitored during recruitment, and every effort will be made to broaden the age distribution across the Pathogen "X" disease severity spectrum.

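### Section 7.3 expects 1,000 contacts in Group 2 alone, which implies a study of 1,500 to 1,667 against a stated joint maximum of 1,000 and leaves the size of Group 1 undetermined

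*Protocol*

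**What the plan says.** **Joint maximum.** The Protocol Summary's population entry gives up to 1,000 participants, covering people with "possible or definitive infection and/or close contacts to patients with possible or definitive infection with Pathogen" X, to be placed in one of two groups. The schematic repeats it: "Total N: Up to 1,000 participants enrolled into one of two patient groups". Section 4 says the study will "evaluate the innate and adaptive immune responses from up to 1,000 study participants", then lists both groups as the types of participant. Section 5.1 also uses up to 1,000, but as the number screened in order to enrol.

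**Group 2.** Section 7.3 anticipates that "the study will enroll 1000 participants in Group 2 (i.e., an average of 1.5 to 2 close contacts per patient" enrolled in Group 1).

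**Group 1.** No section states a number. Section 7.3 gives only its enrolment and follow-up times, and those are placeholders.

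**Basis of the size.** Section 7.1 opens its target with "To address its objectives with adequate power, the study will target enrolling approximately 1,000 Pathogen" and goes on to name both groups in the same sentence. Section 5.1 says that "sample size is based on feasibility instead of power for hypothesis testing". Section 7.1 also sets out the primary statistical analysis of Group 1 data, by the most severe level of care received. A footnote in the Protocol Summary allows the number of participants to be adjusted for the pathogen.

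**The concern.** The same figure, 1,000, is the ceiling for the whole study in three places and the expected size of one group in a fourth. Taken literally, the two leave nobody for Group 1. With the contact ratio that Section 7.3 supplies, they put the study well over its ceiling.

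Group 1 bears the cost. Contacts are to be enrolled as soon as possible after their index case, so the two groups fill together. A study that stops at 1,000 in total would reach far fewer cases than a reader of Section 7.3 would expect, if the anticipated ratio holds. The main comparisons, across levels of care and by age, are made within Group 1. Whoever fills in the Section 7.2 tables also needs to know which Group 1 size applies.

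**Working it through.** **Inputs.** Joint maximum 1,000 (Protocol Summary, schematic, Section 4). Group 2 = 1,000 and contacts per case k = 1.5 to 2 (Section 7.3). Missing assay data 15% (Section 7.2).

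**1. Does Section 7.3 reproduce the stated total?** Group 1 = Group 2 / k, and total = Group 1 + Group 2.
- k = 2: Group 1 = 1,000 / 2 = 500; total = 1,500, which is 50% over 1,000.
- k = 1.5: Group 1 = 1,000 / 1.5 = 667; total = 1,667, which is 67% over.

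The stated total is not reproduced.

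**2. What does the maximum allow at the same ratio?** Group 1 = 1,000 / (1 + k).
- k = 2: Group 1 = 1,000 / 3 = 333; Group 2 = 667.
- k = 1.5: Group 1 = 1,000 / 2.5 = 400; Group 2 = 600.

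**3. Do other readings reconcile the figures?**
- Keep the maximum and 1,000 contacts: Group 1 = 1,000 − 1,000 = 0.
- Read the Section 7.1 target as Group 1 alone: 1,000 contacts gives a ratio of 1,000 / 1,000 = 1.0, outside 1.5 to 2. Keeping the ratio gives 1,500 to 2,000 contacts. Either way the total exceeds the maximum.

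No reading satisfies the maximum, the Group 2 figure and the ratio at once.

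**4. Size of the difference for Group 1.** Evaluable = 0.85 × Group 1. Confidence-interval width scales with 1/√n. The half-width shown is for a response rate of 50% (normal approximation), 1.96 × √(0.25 / evaluable).

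| | k = 2 | k = 1.5 |
|---|---|---|
| Group 1 implied by Section 7.3 | 500 | 667 |
| Group 1 at the maximum | 333 | 400 |
| Reduction | 1 − 333/500 = 33% | 1 − 400/667 = 40% |
| Evaluable, Section 7.3 | 425 | 567 |
| Evaluable, maximum | 283 | 340 |
| Interval widening | √(500/333) = 1.22 | √(667/400) = 1.29 |
| Half-width, Section 7.3 (percentage points) | 4.8 | 4.1 |
| Half-width, maximum (percentage points) | 5.8 | 5.3 |

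**5. Illustration by level of care.** Assume three care levels of equal size, which the protocol does not state. Take a two-sided 5% test with 80% power, and a two-sample t-test with n multiplied by 0.955 to approximate the Wilcoxon test. The detectable standardized difference between two levels is then 0.38 to 0.42 at the maximum, against 0.30 to 0.34 under Section 7.3. Unequal care levels would change these values.

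**The case against.** The best defence is that this is a shelf-ready protocol for a pathogen not yet known. The footnote in the Protocol Summary foresees adjusting the number of participants, Section 7.3 only anticipates its figure, and Section 7.2 calls the primary and secondary analyses mostly exploratory. A pathogen-specific revision of the size is therefore to be expected. That bears on how much harm follows, but it does not remove the contradiction. The 1,000 and the 1.5 to 2 are filled in, in a section that marks its real unknowns with X. Permission to change a number later does not make the present numbers agree, and an anticipated figure still cannot exceed the study's own maximum by half or more.

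Other parts of the defence stand, and they limit the point:
- A reader might infer that the power or precision in Section 7.2 is wrong. The tables there have no results, and they are indexed by n, so once filled they hold for any group size. Only the applicable column changes.
- A reader might fault the correlation grid for stopping at n = 150. Section 7.2.1 allows correlations in subsets as well as in the whole cohort. Under the equal-thirds assumption the evaluable sizes per care level at the maximum, 283/3 = 94 to 340/3 = 113, lie inside the grid.
- A reader might say that all four primary objectives rest on Group 1. The objectives refer to study subjects or name no group, and Section 2.2.2 gives contacts a part in the immunology. What Section 7.1 supports is narrower: Group 1 data by level of care form the primary statistical analysis.

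**Conclusion.** The contradiction is real and follows from the protocol's own figures. Section 7.3 implies 1,500 to 1,667 participants, 50 to 67% above the joint maximum, and no reading of the several 1,000s removes the conflict. Depending on which statements are kept, Group 1 is 0, 333 to 400, 500 to 667, or about 1,000.

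The contrast of 333 to 400 with 500 to 667 assumes that the anticipated contact ratio holds and, for the smaller range, that enrolment stops at 1,000 in total. The evaluable counts also assume the plan's 15% missing. The detectable differences by care level are illustrative only.

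This is an inconsistent enrolment plan and not a failed power calculation, since the protocol states no power that could fail. It still has to be corrected before activation, because the planned size of the group in the primary statistical analysis cannot be determined from the document. The clash between Sections 7.1 and 5.1 over power and feasibility is a separate, smaller wording conflict about the same number.

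**What to change.** State one total and one Group 1/Group 2 split, in the same terms, in the Protocol Summary, the schematic and Sections 4, 5.1, 7.1 and 7.3. In Section 5.1, say whether the number is screened or enrolled. The sponsor must choose between two routes:

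- **The maximum of 1,000 stands.** Restate Section 7.3 as about 333 to 400 Group 1 participants and 600 to 667 contacts. Use those sizes, with 283 to 340 evaluable in Group 1, when the Section 7.2 tables are filled. This changes wording only and adds no participants, but the stated precision for Group 1 is less favourable than Section 7.3 now suggests.
- **1,000 contacts are intended.** Correct the total to 1,500 to 1,667 everywhere. That means 500 to 667 participants more than the current maximum, with the corresponding site, laboratory and budget load.

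If neither fits, the contact ratio itself should be revised and the sizes recalculated from it.

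On either route, align Section 7.1 with Section 5.1. Either describe the size as set by feasibility and report the precision it gives, or state the effect sizes for which it is considered adequate.

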7.4 Analysis Plan

All data from enrolled patients will be analyzed. Most primary and secondary analyses will be performed using SAS and R statistical software. This section provides an overview of statistical approaches that will be used to perform data analysis.

7.4.1 Analysis Variables

The analysis variables consist of participant characteristics, such as demographics/ sociodemographics and medical history (including pre-existing conditions, new acute or chronic medical conditions, and concomitant medications), presentations Pathogen “X” infection (including the clinical course of disease), immunogenicity for primary, secondary, and exploratory objective analyses, and host genetics.

7.4.2 Analysis of Primary and Secondary Endpoints

The statistical analysis for the primary and secondary objectives of the study will seek to answer key questions related to the immune responses and clinical course of Pathogen “X” infection.

The study will not randomize patients between study arms. Therefore, in order to account for potential confounders, statistical analyses will either be stratified by group or seek to adjust for covariates where deemed appropriate. For example, some analyses will be stratified by study arm (e.g., Groups 1 and 2). Other analyses will be stratified or adjust for age (treated as continuous or categorical variable), sex, for example.

Categorical variables (e.g., disease severity, binary responses, participants’ characteristics at enrollment) will be analyzed by tabulating the relative frequency of each category by group and time point, as appropriate. Crude response rates will be presented with their 95% confidence interval estimates calculated using the score test.¹² Fisher’s exact tests will be used to compare response rates between two groups. Because participants enrolled in distinct groups may differ in terms of demographic variables and comorbidities, many of the statistical analyses will compare response rates between groups using binary logistic regression to adjust for potential confounders (e.g., age, gender, race, comorbidities).

Continuous variables will be analyzed using univariate and bivariate descriptive statistics to summarize data by group, time point, gender, and race, for example. Data will be visualized using graphical techniques, including boxplots, density estimates, scatterplots, heatmaps, and networks. Comparisons of two independent groups will be performed using a nonparametric Wilcoxon rank sum test. To compare more than two groups, we will first use a Kruskal-Wallis or an F-test (depending on the normality assumption) to test for overall differences. Should the overall test reach statistical significance at the 2-sided 0.05 level, individual (post-hoc) pairwise tests will be performed (e.g., using Dunn’s procedure following a Kruskal-Wallis’ test). Comparisons of paired data will be accomplished using the Wilcoxon signed-rank test or paired *t*-test. In addition, since participants are not randomized between groups at enrollment, some of the statistical analyses will use multiple linear regression to compare groups while adjusting for potential confounders (e.g., age, gender, race, comorbidities). Longitudinal data will be analyzed using statistical methods for repeated measures and dependent data (e.g., mixed-effects models,¹³ generalized estimating equations (GEE).¹⁴ Similar modeling approaches will be considered to account for potential intra-close contact correlations in analyses that involve data from Group 2. Preliminary data transformations (e.g., logarithmic, square root) may be

performed in regression analyses to better satisfy assumptions of symmetry and homoscedasticity (constancy of variance).

If the frequency of missing data is substantial, statistical analyses may be performed using parametric models fitted using the method of maximum likelihood. This approach is robust when data are missing at random (MAR). MAR assumes that the probability of an observation being missing may depend upon the observed responses and observed covariates, but it does not depend on any unobserved factors. This assumption is less stringent than the missing completely at random (MCAR) assumption. If measurements of immune responses are left- and/or right-censored, we will use Hughes’ linear mixed effects models to accommodate censoring in analyses of repeated measures.¹⁵ Analyses of repeated immunogenicity measurements may be done using weighted GEE methods,¹⁶ which are valid under MAR.

To visualize multivariate immune response variables, we may use dimensionality reduction techniques (e.g., principal component analysis, multidimensional scaling, Uniform Manifold Approximation and Projection), and perform unsupervised learning (e.g., k-means, model-based clustering) to identify subgroups of participants with similar immune profiles.

Where appropriate (e.g., in transcriptional analysis), we will perform formal p-value adjustment for multiple comparisons. We will control either the family-wise error rate (FWER) using the Holm-Bonferroni procedure¹⁷ or the false discovery rate (FDR) using the Benjamini-Hochberg or the Benjamini-Yekutieli procedures.^{18,19} The selection of a method for p-value adjustment may depend on the objective of the statistical analysis.

Some of the primary and secondary analyses will seek to identify predictive signatures of categorical outcome variables (e.g., disease severity) using a combination of demographic (e.g., age, race), clinical (e.g., comorbidity), and laboratory (e.g., viral load, immune responses) variables. We will first build candidate predictive models using multiple regression techniques (e.g., binary logistic regression for binary endpoints) modeling the probability of a particular event (e.g., disease progression, hospitalization) as a function of a set of predictors, while adjusting for potential confounding factors, as appropriate). Models may be fitted using regularization techniques (e.g., lasso, elastic net) and cross-validation to identify optimal tuning parameters. Where appropriate, we will assess the predictive power of candidate signatures using doubly (nested) cross-validated receiver operating characteristics (ROC) curves.

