3. OBJECTIVES

3.1 Study Objectives Endpoints (Outcome Measures)

Table 1: Objectives and Endpoints (Outcome Measures)

Objectives	Endpoints
Primary	

 To characterize Pathogen “X” binding and neutralizing antibody responses by age and disease severity in study subjects 	
 Pathogen “X” neutralization assay (e.g., PRNT, FRNT) Pathogen “X” pseudoneutralization assay

 To characterize T cell responses by age and disease severity 	
 T cell ELISpot and/or ICS assays

 To characterize B cell responses by age and disease severity 	
 Memory B cell testing Plasmablast antibody secreting cells (ASCs) responses

 To describe the clinical presentation and outcomes of Pathogen “X” infection in study subjects 	
 Clinical symptoms, laboratory abnormalities, days of illness, residual clinical problems, survival/death
Secondary	

 To describe innate immune responses to Pathogen “X” 	
 Transcriptomics, flow cytometry, serum and/or culture supernatant cytokine ELISA

 To collect specimens for isolation of Pathogen “X” from body compartments pertinent to the pathogen 	
 PCR and/or cultures

 To determine rates of Pathogen “X” infection among close contacts of infected patients enrolled in Group 1 	
 Rates of Pathogen “X” detection among close contacts of infected enrolled subjects at enrollment and over follow-up

 To determine the persistence of Pathogen “X” in whole blood, serum, urine, saliva, stool, or other body fluids as available (e.g., semen, vaginal secretions, breast milk) and characterize modes of pathogen shedding to support the development of diagnostic assays and public health prevention policy around transmission risk 	
 Repeated PCR and/or cultures

Objectives	Endpoints
Exploratory	

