7.2.2 Power Analysis for Response Rates

The immune responses will also be analyzed by estimating response rates in Group 1 overall and in subgroups of Group 1 participants defined by baseline subject characteristics such as age and disease severity. Examples of response rates include the proportion of XXX. The study may also estimate the rate of Pathogen “X” infection among Group 2 participants, i.e. close contacts of Pathogen “X”-positive enrolled subjects.

The precision with which the true response rate can be estimated from the observed data depends on the true underlying response rate and the sample size (n). Two-sided 95% confidence intervals for the response rate based on observing a particular rate of response are presented in Table X for a variety of scenarios.

Table X: Two-sided 95% confidence intervals for the true response rate based on observing a particular rate of responses

Sample size	Number of responses	Response rate	95% confidence interval (in %)

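### The score interval stated for crude rates does not allow for clustering of contacts within index cases, so it is too narrow for the Group 2 infection rate if infection is correlated within an index case

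*Protocol*

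**What the plan says.** Three statements in the protocol bear on this.

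- **Interval method.** Section 7.4.2, in its paragraph on categorical variables: "Crude response rates will be presented with their 95% confidence interval estimates calculated using the score test". No exception is made for Group 2.
- **What counts as a rate.** Section 7.2.2, on the precision of response rates, begins with immune response rates in Group 1. It then adds that the study may estimate the rate of "infection among Group 2 participants, i.e. close contacts of Pathogen" X-positive subjects. Its 95% interval table follows and serves for rates in general. Section 3.1 lists the rate of "infection among close contacts of infected patients enrolled in Group 1" as a secondary objective.
- **Correlation.** Section 7.4.2, at the end of its passage on repeated measures (mixed-effects models, GEE): "Similar modeling approaches will be considered to account for potential intra-close contact correlations in analyses that involve data from Group 2".

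Section 7.3 gives the cluster size: "an average of 1.5 to 2 close contacts per patient enrolled in Group 1".

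**The concern.** A binomial score interval takes every contact as an independent observation. Group 2 is not sampled that way. Contacts enter because a particular index case was enrolled, and contacts of one case share that case's infectiousness and part of the exposure. Section 6.3 records room sharing, days of exposure and quarantine measures, and these will tend to be alike within a household. Positive correlation within an index case is therefore the natural expectation, although the protocol gives no value for it.

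The two statements in Section 7.4.2 differ in force. The score interval is definite. The allowance for correlation is only to be considered, and it concerns modelling, whereas the crude rate and its interval are not modelled. The term used for the correlation is also unclear: it could mean repeated measurements on one contact, or different contacts of one index case. An analyst who followed the text as written could report the unadjusted interval for this objective and be within the plan.

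**Working it through.** **Figure to reproduce.** There is none. The rate table in Section 7.2.2 is an unfilled template, and no contact infection rate is given.

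**Inputs from the protocol.** Two-sided 95% interval; score method; mean contacts per index case m = 1.5 to 2; Group 2 size. Section 7.3 gives 1,000 for Group 2, while the study total is capped at 1,000. With 2 contacts per case, a total of 1,000 gives 1,000 × 2/3 = 667 contacts around 333 index cases. Both sizes are shown.

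**Assumptions, not in the protocol.** Infection rate 20%; ICC 0.1, 0.3 or 0.5; coefficient of variation (CV) of cluster size 0, 0.5 or 0.7.

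**Step 1: the interval as stated.** With p = 0.20 and z = 1.96, the limits are [p + z²/2n ± z√(p(1−p)/n + z²/4n²)] / (1 + z²/n).

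- n = 667: 17.1% to 23.2%
- n = 1,000: 17.6% to 22.6%

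**Step 2: design effect and coverage.** DE = 1 + [m(1 + CV²) − 1] × ICC. The approximate coverage of the unadjusted interval is 2Φ(1.96/√DE) − 1. For example, with m = 2, CV = 0.7 and ICC = 0.3: DE = 1 + (2 × 1.49 − 1) × 0.3 = 1.594, √DE = 1.263, coverage 87.9%.

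| m | CV | ICC 0.1: DE, coverage | ICC 0.3: DE, coverage | ICC 0.5: DE, coverage |
|---|---|---|---|---|
| 2 | 0 | 1.10, 93.8% | 1.30, 91.4% | 1.50, 89.0% |
| 2 | 0.5 | 1.15, 93.2% | 1.45, 89.6% | 1.75, 86.2% |
| 2 | 0.7 | 1.20, 92.7% | 1.59, 87.9% | 1.99, 83.5% |
| 1.5 | 0 | 1.05, 94.4% | 1.15, 93.2% | 1.25, 92.0% |
| 1.5 | 0.5 | 1.09, 94.0% | 1.26, 91.9% | 1.44, 89.8% |
| 1.5 | 0.7 | 1.12, 93.6% | 1.37, 90.6% | 1.62, 87.7% |

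**Step 3: simulation check.** Beta-binomial data, 4,000 runs per setting, cluster size 1 + Poisson (CV 0.5 at a mean of 2, just under 0.5 at a mean of 1.5). Coverage at ICC 0.1, 0.3 and 0.5:

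- 333 index cases, mean 2: 93.2%, 89.2%, 86.2%
- 500 index cases, mean 2: 93.8%, 90.6%, 86.5%
- 400 index cases, mean 1.5: 94.0%, 91.1%, 90.3%

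These agree with the formula to within about one percentage point. In the same kind of simulation, an intercept-only logistic GEE with robust variance covered 94–96% in every setting.

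**Step 4: effect on the reported limits.** Score interval on n/DE at 20% infected:

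| n | as stated | DE 1.5 | DE 1.99 |
|---|---|---|---|
| 667 | 17.1–23.2% | 16.5–24.0% | 16.1–24.6% |
| 1,000 | 17.6–22.6% | 17.1–23.2% | 16.7–23.7% |

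Width grows by about √DE: 1.22 times at DE 1.5 and 1.41 times at DE 1.99.

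**The case against.** The strongest reply is that Section 7.4.2 already covers this. Its sentence on correlation extends to any analysis of Group 2 data and is not confined to continuous outcomes, and GEE handles binary outcomes. A reader might infer that the protocol simply treats contacts as independent. The text does not support that, because it recognises the dependence. What it does not do is commit to handling it, or say that the score interval gives way for this rate.

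A second reply is that Section 7.4 calls itself an overview and that a statistical analysis plan, not shown here, would choose the estimator. That would answer a complaint of missing detail. Here, however, a method is stated, and it is the one that does not fit clustered contacts. It is also fair that the link from the contact rate to the score interval is read from Sections 7.2.2 and 7.4.2 together. Section 7.2.2 says only that the study may estimate this rate, and no sentence says that the crude interval will be the only one reported.

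Third, the effect may be small. At an ICC of 0.1 coverage is 93–94%. With equal clusters and 1,000 contacts, the limits move by at most about 0.6 percentage points even at an ICC of 0.5. The study is descriptive and sized on feasibility. This stands, and it limits the weight of the point.

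Two further inferences should be avoided. The Section 7.2.2 table does not overstate precision, because it is still empty. And the purpose of informing public health policy on transmission risk belongs to the objective on persistence and shedding, not to the contact infection rate.

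**Conclusion.** The point holds in a conditional form. The only interval the protocol states for rates assumes independent contacts. If infection is positively correlated within an index case, and this interval is the one reported, it is too narrow for a secondary objective.

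At a 20% rate and a mean of 2 contacts, coverage is about 93–94%, 88–91% and 84–89% at ICC 0.1, 0.3 and 0.5, with the lower ends belonging to the most unequal clusters. At a mean of 1.5 contacts it is about 94%, 91–93% and 90–92% for cluster-size CVs up to about 0.5, and a little lower at 0.7. The rate, the ICCs and the spread of cluster sizes are all assumptions. With an ICC of zero there is no loss.

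The shortfall is negligible to moderate and would not overturn a descriptive finding. It is worth correcting because this shelf-ready text would carry the same interval into an activated study.

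**What to change.** Reconcile the two statements in Section 7.4.2. Say that the 95% interval for Group 2 infection rates is clustered on the index case, and name the method. Either of these would do:

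- an intercept-only logistic GEE with robust variance, which under an independence working correlation leaves the crude rate itself unchanged; or
- a score interval computed on n divided by the design effect.

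Say also that the correlation meant is between contacts of the same index case, in addition to any correlation between repeated measurements on one contact. When the Section 7.2.2 table is filled in at activation, show any Group 2 rows over a range of assumed design effects, since the ICC for an unidentified pathogen cannot be known now.

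The cost is a sentence or two and a standard procedure in SAS or R, using a method the protocol already cites. The downside is a modestly wider interval: about 2% to 22% wider with equal clusters over ICC 0.1 to 0.5, and up to about 41% wider with strongly unequal clusters at an ICC of 0.5.
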